	
sexual intercourse while in the study and for at least 1 month after the last study drug application.
 
8. Women of child-bearing potential must be nonlactating and have negative pregnancy test results at Screening (serum) and on Day 1 before study drug administration (urine).
 
9. Subject is reliable and capable of adhering to the protocol and visit schedule, in the investigator's judgment, and has signed informed consent/assent, as applicable.
 
10. Subject is taking no more than 3500 IU/day Vitamin A (e.g., as in a multivitamin).
 
Exclusion criteria:
 
1. Subject has any variant of ichthyosis other than LI or another disorder of keratinization, including syndromic ichthyoses.
 
2. Subject has current moderate or severe stinging/burning at Screening.
 
3. Subject has an ongoing cutaneous infection or any other significant concomitant skin disease (other than the LI) which, in the investigator's opinion, may interfere with the study assessments.
 
4. Subject with a known lipid disorder (hypertriglyceridemia >200 mg/dL, hypercholesterolemia >250 mg/dL) unless well controlled by stable doses of lipid-lowering agents for at least 6 months.
 
5. Subject was previously treated with trifarotene/CD5789 in an acne or ichthyosis study.
 
6. Subject has any other significant concomitant disease, or poorly controlled medical condition other than LI that in the investigator's opinion may put him or her at risk if he or she takes part in the study, and/or that may interfere with the study assessments..
 
7. Subject has a medical condition that potentially alters bone metabolism (e.g., osteoporosis, thyroid dysfunction, Cushing syndrome, Crohn's disease, or ulcerative colitis).
 
8. Subject is being treated for major depression disorder and/or has a history of major depression or suicide attempt requiring hospitalization, medications, and close psychiatric surveillance to prevent suicide attempts.
 
9. Subject with positive serology for hepatitis B surface antigen, hepatitis C, or are known to be HIV positive or to have AIDS at Screening.
 
10. Subject with any of the following laboratory values at Screening:
 
 Aspartate aminotransferase or alanine aminotransferase $>1.5 \times$ upper limit of normal defined by the laboratory Total bilirubin >1.1 mg/dL or, in case of Gilbert's syndrome, total bilirubin >3 mg/dL Hemoglobin <12.5 g/dL for men and <11.5 g/dL for women Platelets $<150 \times 10^9/L$ or $>400 \times 10^9/L$ 
11. Subject has any clinically other significant abnormal laboratory value (hematology, chemistry, or urinalysis) at Screening that, in the investigator's opinion, may put the subject at risk if he or she takes part in the study, and/or that may interfere with the study assessments.
 
12. Subject has had recent systemic malignancy (e.g., within 5 years) with exception of nonmelanoma skin cancer or cervical intraepithelial neoplasia of Grade 1 who are >6 months post-treatment.
 
13. Subject has a history of long QT syndrome or clinically significant electrocardiogram (ECG) abnormalities, including clinically significant conduction disorders or significant arrhythmias, QTcF interval >450 ms, PR interval is not between 120 and

--	---

	
220 ms (inclusive), HR >100 bpm or <50 bpm, QRS interval >110 ms, or QT intervals that cannot be consistently analyzed.
 
14. Subject has a known allergy or sensitivity to any of the components of the investigational products.
 
15. Subject has been exposed to excessive ultraviolet (UV) radiations on the treated zones within 1 month before Baseline visit or is planning intensive UV exposure during the study (e.g., occupational exposure to the sun, sunbathing, phototherapy, etc.).
 
16. Subject is inherently sensitive to sunlight.
 
17. Subject is unable or unwilling to stop use of topical or systemic retinoids.
 
18. Subject is presumed to be abusing drugs or alcohol at Screening or Baseline Visits based on medical history or current clinical symptoms.
 
19. Subject is participating in another interventional clinical trial.
 
20. Subject is institutionalized.
 
21. Subject is in any way related to the sponsor, investigator, or site personnel.

INVESTIGATIONAL PRODUCT	
Name: Trifarotene (CD5789) cream HE1
 
Double-blind Period dose, route, frequency: A fixed dose (up to 36 g per dose, determined at Visit 2) of 100 µg/g or 200 µg/g applied topically twice weekly on up to 90% BSA
 
Open-label Extension dose, route, frequency: A fixed dose (up to 36 g per dose, determined at Visit 2) of 200 µg/g applied topically twice weekly on up to 90% BSA

REFERENCE PRODUCT(S)	
Name: Vehicle cream
 
Double-blind Period dose, route, frequency: A fixed dose (up to 36 g per dose, determined at Visit 2) applied topically twice weekly on up to 90% BSA

TREATMENT REGIMENS	
Topical application twice weekly to all affected skin except the scalp, axillae, and inguinal area.

COORDINATING/ PRINCIPAL INVESTIGATOR	
[name] Department of Dermatology, Yale University School of Medicine [name]

PLANNED STUDY SITES	
Approximately 40 sites across North America, Europe, Israel, and Australia


CRITERIA FOR EVALUATION
	
Primary efficacy endpoint: The proportion of subjects in each treatment group who experience successful resolution of LI where “success” is defined as clear/almost clear on treated areas and at least a 2-grade change from Baseline at Week 12/end-of-treatment (EOT) in the Double-blind Period on the 5-point IGA full body scale.
 
Secondary endpoints:
 
 – The difference in mean scores between the active trifarotene cream HE1 and vehicle groups in the following assessment indices from Baseline through Week 12: 
 – 5-point Visual Index for Ichthyosis Severity (VIIS) for scaling from Baseline through Week 12 (overall 16 points for scaling, i.e. 0-4 points for 4 body areas: chest/abdomen, back, arms and legs) – Individual score for roughness (Scale: 0–4) overall – Palm/sole Assessment (Scale: 0–4) – Quality of life per Dermatology Life Quality Index (DLQI) and children’s DLQI (cDLQI) – The difference in proportion of subjects with presence of fissures on palms/soles (presence/absence, number of fissures, and pain associated with fissures on a 0-3 scale) at Week 12 between the active trifarotene cream HE1 and vehicle groups 
Exploratory endpoints:
 
 – The difference in mean ectropion (Ectropion Severity Score [ESS] of 0–8) scores between the active trifarotene cream HE1 and vehicle groups from Baseline through Week 12 – The difference in quality of life per EQ-5D-5L and EQ-5D-Y score between the active trifarotene cream HE1 and vehicle groups from Baseline through Week 12 
Safety endpoints:
 
 – Reported serious adverse events (SAEs), treatment-emergent AEs (TEAEs), and changes in clinical laboratory tests, vital signs, physical examinations, and 12-lead ECGs – Local tolerability (Scale: 0-3 [none, mild, moderate, severe], determined by the investigator) for each body area (chest/abdomen, back, legs, arms, and face/neck). 
Pharmacokinetic endpoints: Plasma concentrations of CD5789 and its major metabolites will be measured.


STATISTICAL METHODS
	
Analysis Populations:
 
The following are planned for the Double-blind Period of the study:
 
The Safety population will be the primary population for analyses of safety and tolerability and will comprise all subjects who are randomized to treatment and receive at least 1 application of study drug.
 
The intent-to-treat (ITT) population will comprise all randomized subjects. This population will be used as the primary population for the analysis of efficacy for the Double-blind Period of the study.
 
The modified intent-to-treat (mITT) population comprises all subjects in the safety population with at least 1 postbaseline assessment of efficacy in the Double-blind Period. This population will be used as the primary population for the analysis of efficacy for the Double-blind Period of the study.
 
The per protocol (PP) population will be defined prior to database lock and will comprise subjects in the mITT population who met all inclusion criteria and no exclusion criteria,


were compliant with study drug application, and who had no significant protocol deviations.
 
The PK population includes all subjects in the Safety Population who have at least 1 plasma sample with quantifiable concentration. The PK population will be used to summarize all PK endpoints.
 
The following populations are planned for the OLE of this study:
 
The OLE Safety population: all subjects who complete the 12-week Double-blind Treatment Period and receive at least 1 application of study drug in the OLE.
 
OLE ITT population: all subjects who complete the 12-week Double-blind Period and who sign the OLE informed consent.
 
The OLE mITT population: all subjects in the OLE safety population with at least 1 assessment of efficacy after Visit 6.
 
The OLE PP population: all subjects in the OLE mITT population who met all inclusion criteria and no exclusion criteria, were compliant with study drug application from baseline through EOT, and who had no significant protocol deviations throughout the study.
 
Subject Characteristics and Disposition: Descriptive statistics will be used to summarize demographic characteristics (age, sex, ethnicity, and race) and baseline characteristics for all enrolled subjects. Medical history, physical examination findings, and vital sign measurements for all randomized subjects will be presented in listings.
 
Efficacy Analyses: The number and proportion of subjects in each treatment group with successful resolution of LI by Week 12/EOT in the Double-blind Period will be presented. The primary efficacy endpoint will be analyzed using a logistic regression model with treatment and age group as factors. Other baseline characteristics and interactions may be included. The odds ratios and 95% CIs for the odds ratios will be presented. The difference in proportions between the active trifarotene cream HEI and vehicle cream groups, 95% CIs for the differences, and P-values for the differences in treatment will also be presented.
 
The IGA scores as well as secondary and exploratory efficacy endpoints will be analyzed by visit using descriptive statistics through Week 24. Change from Baseline through Week 12 will be presented and analyzed using a mixed model for repeated measures (MMRM). The model will include the change from Baseline score as the dependent variable, treatment group as a fixed effect, subject as a random effect, and Baseline score value as a covariate. Frequencies of results and 95% confidence intervals will also be reported, and scores will be analyzed as categorical variables using the Cochran-Mantel-Haenszel test. For subjects who report having fissures, the number of fissures and pain related to fissures will also be presented on a scale of 0-3 (none, mild, moderate, severe).
 
Clinical Pharmacology Analyses: Noncompartmental PK analysis will be performed for the PK subset of subjects, as data permit. Plasma concentrations of CD5789 and its major metabolites will be measured and will be listed by subject.
 
Safety Analyses: Safety and tolerability will be assessed based on the incidence of reported TEAEs, and SAEs, including relationship to study drug and severity, as well as physical examination findings, vital sign measurements (supine systolic blood pressure [SBP] and diastolic blood pressure [DBP] and pulse), clinical laboratory results (hematology, including serum aminotransferases and serum lipids, coagulation, clinical chemistry, and urinalysis) and 12-lead ECGs. Descriptive statistics for observed values and change from Baseline will be calculated at each visit within each study period and by treatment group within cohort.

--

SAMPLE SIZE DETERMINATION	The first cohort of 15 adult subjects is a reasonable sample size to assess safety and tolerability before enrolling adolescents. Accounting for a 20% drop-out/nonevaluable rate, a total sample size of 120 subjects randomized in a 1:1:1 ratio to 2 active trifarotene cream HE1 arms and a vehicle cream arm will provide >80% power to detect a difference between each separate trifarotene cream HE1 arm (32 evaluable subjects) and the vehicle cream arm (32 evaluable subjects) 2-sided Fisher's Exact Test assuming a 70% success rate and a 40% success rate, respectively.. This study is not powered to detect a difference between the 2 active arms.
STUDY AND TREATMENT DURATION	
The sequence and maximum duration of the study will be as follows:
 
 1. Screening: Up to 35 days (after signing informed consent, if necessary, washout may be up to 3 months, and subjects should return to the site after washout to complete the study eligibility requirements). 2. Double-blind study drug application: Twice weekly for up to 12 weeks. 3. Optional Open-label Extension: Twice weekly for up to 12 weeks. 4. Follow-up: 14 days after last study drug application. 
The maximum study duration for each subject is approximately 229 days (33 weeks).
 
The maximum treatment duration for each subject is 24 weeks.

2.2. Schedule of Events

Table 2-1: Schedule of Events for Double-blind Period

	Screening (-35 days to -1 day) Washout up to 3 months ^a	Double-blind Treatment Period						
		Baseline (Day 1)	Telephone Visit (Day 7)	Day 14 ± 5 days	Day 30 ± 7 days	Telephone Visit (Day 45)	Day 60 ± 7 days	Day 90 ^{b,c} ± 7 days (ET)
Visit	1	2		3	4		5	6
Week		1		2	4		8	12
Written informed consent/assent	X							X ^a
Assign screening number	X							
Inclusion/exclusion criteria	X	X						
Demographics	X							
Medical history	X							
Physical examination	X	X ^d						X ^c
Vital signs (blood pressure and pulse)	X	X		X	X		X	X
Height, weight, and BMI	X							X
IGA assessment ^e	X	X		X	X		X	X
VIIS ^f assessment	X	X		X	X		X	X
Roughness assessment ^g	X	X		X	X		X	X
Palm/sole assessment	X	X		X	X		X	X
Palm/sole fissuring assessment ^h	X	X		X	X		X	X
Ectropion score	X	X		X	X		X	X
Photographs ⁱ		X			X			X
Quality of life per Dermatology Life Quality Index (DLQI)		X		X	X		X	X

	Screening (-35 days to -1 day) Washout up to 3 months ^a	Double-blind Treatment Period						
		Baseline (Day 1)	Telephone Visit (Day 7)	Day 14 ± 5 days	Day 30 ± 7 days	Telephone Visit (Day 45)	Day 60 ± 7 days	Day 90 ^{b,c} ± 7 days (ET)
Visit	1	2		3	4		5	6
Week		1		2	4		8	12
EQ-5D Quality of Life Questionnaire		X		X	X		X	X
12-lead ECG ^l	X	X			X			X
Clinical laboratory tests (hematology, chemistry, urinalysis) ^k	X	X			X			X
Serology (hepatitis B surface antigen, hepatitis C)	X							
Pregnancy test for female subjects (serum at Screening; urine subsequently) ^l	X	X			X		X	X
Randomization via IWRS		X						
PK blood sample collection ^m		X		X	X		X	X
Initial study drug application by clinic staff and measurement ⁿ		X						
Application instructions, advice on emollient and sunscreen use		X	X	X	X	X		
Dispense study drug and diaries ^o		X ^p		X	X		X	
Concomitant medications	X	X	X	X	X	X	X	X
Tolerability assessment		X		X	X		X	X
Adverse events (and review diaries)		X	X	X	X	X	X	X
Collect all used/unused study drug ^q				X	X		X	X
Provide information about OLE option					X	X	X	

Abbreviations: BMI = body mass index; DLQI = Dermatology Life Quality Index; ECG = electrocardiogram; ET = early termination; HEENT = head, eyes, ears,

nose, throat; ICF = informed consent form; IGA = Investigator's Global Assessment; IWRS = interactive web response system; OLE = open-label extension; PK = pharmacokinetic; WOCBP = women of childbearing potential; VIIS = Visual Index for Ichthyosis Severity

- a. Upon signing informed consent and entering the Screening Period, subjects will stop using physical and medical treatments for LI, including balneotherapy, and may begin to washout prohibited topical and systemic treatments with designated washout periods, as applicable. Washout may be up to 3 months, as necessary. During washout, subjects may continue taking usual care of visible skin (face and scalp) for cosmetic reasons and of extremities (hands and feet) to avoid functional consequences on walking or moving their fingers. Subjects may shower but not bathe or swim during the Screening Period. After completing any necessary washout of prohibited medications, subjects will return to the site to complete the study eligibility requirements.
- b. Day 90 procedures should be conducted for subjects who terminate the study early. If a subject discontinues IP, but continues to attend clinic visits, Day 90 will occur as scheduled. Day 90/Week 12 will be the first visit of the OLE for subjects who choose to continue (subjects will have up to 7 days to decide to sign the ICF and begin the OLE). Subjects who decide to continue into the OLE will have the following additional procedures: 1) sign informed consent; 2) will be weighed; 3) will be instructed on study drug application; 4) will be given new diaries, and 5) will be provided with study drug.
- c. A Follow-up telephone call will be made within 14 days after Day 90 to subjects who choose not to continue into the OLE.
- d. Limited physical examination to include HEENT, cardiorespiratory, abdomen, range of motion.
- e. IGA: 0 = clear; 1 = almost clear; 2 = mild; 3 = moderate; 4 = severe.
- f. VIIS scale for each body area: chest/abdomen, back, legs, and arms, for a possible overall score = 16.
- g. Roughness (0-4 scale);
- h. Palm/sole fissuring assessment: present/absent/number/pain (0-3 scale).
- i. Photography will be performed at sites with the capability for subjects who sign a photographic ICF. A central reader who will not be an investigator in the study will review the photographs to assess consistency of investigator scoring of LI severity as a quality check.
- j. ECG to be conducted at Screening, Baseline, Day 30, and Day 90 for all subjects. Subjects in the PK substudy will also have postdose ECGs at each serial blood draw on Day 1 and Day 30.
- k. Subjects must be fasting (i.e., at least 8 hours)
- l. Note: Subjects who are premenstrual at Screening but begin menses during the course of the study should follow the pregnancy testing schedule for WOCBP correlating to the visit menses began.
- m. Samples for PK will be drawn from all subjects at Baseline and at each clinic visit. At selected sites among subjects who consent to participate in the PK substudy, samples will be taken predose and at 1, 2, 4, 8, 12, and 24 hours postdose on Day 1. On Day 30, IP will be applied in the clinic for PK substudy subjects, and PK samples will be taken predose and at 1, 2, 4, 8, 12, and 24 hours postdose. Trough levels will be drawn when the subjects are in the clinic for other study visits (i.e., Day 14, Day 60, and Day 90). Visits for PK must occur at least 24 hours after the last application of the IP to avoid contamination of the blood samples with any IP that may have remained in the skin after the last application.
- n. Study staff will apply initial dose of study drug in the clinic after Baseline measurements, and the amount of study drug used will be measured (i.e., 36-g tube will be measured before and after application to determine amount used) to determine fixed dose.
- o. Study drug provided in 50-g tubes (maximum single application is 36 g). Measure study drug tubes before dispensing; subjects must record days/times of study drug application in the diaries and any areas of skin not treated, e.g., due to local reactions). Dispense enough additional study drug until next visit (except at Day 90, unless subject consents to continue into OLE).
- p. Confirm study drug compliance by measuring tube weight and reviewing diary.

Table 2-2: Schedule of Events for Open-label Extension

	Open-label Treatment Period						Follow-up
	Telephone Visit (Day 97) ^a	Day 104 ± 5 days	Day 120 ± 7 days	Telephone Visit (Day 134)	Day 150 ± 7 days	Day 180 ± 7 days/ET	Day 194 or 14 days after End of Open-label Treatment
Visit		7	8		9	10	11
Week		14	16		20	24	26
Informed consent ^a							
Physical examination ^b						X	X
Vital signs (blood pressure and pulse)			X	X		X	X
Weight	X						
Record IGA ^c		X	X		X	X	X
VIIS ^d assessment		X	X		X	X	X
Roughness assessment ^c		X	X		X	X	X
Palm/sole assessment		X	X		X	X	X
Palm/sole fissuring assessment		X	X		X	X	X
Ectropion score			X	X		X	X
Clinical laboratory tests (hematology, chemistry, urinalysis) ^f			X			X	
Pregnancy test for female subjects (urine) ^g			X		X	X	X
ECG			X			X	
PK blood sample collection ^h			X			X	
Application instructions, advice on emollient and sunscreen use ⁱ	X	X	X	X			

	Open-label Treatment Period						Follow-up
	Telephone Visit (Day 97) ^a	Day 104 ± 5 days	Day 120 ± 7 days	Telephone Visit (Day 134)	Day 150 ± 7 days	Day 180 ± 7 days/ET	Day 194 or 14 days after End of Open-label Treatment
Visit		7	8		9	10	11
Week		14	16		20	24	26
Dispense study drug and diaries ^l		X	X		X		
Concomitant medications	X	X	X	X	X	X	X
Tolerability assessment		X	X		X	X	
Adverse events (and review diaries)	X	X	X	X	X	X	X
Collect all used/unused study drug ^k		X	X		X	X	

Abbreviations: ECG = electrocardiogram; ET = early termination; HEENT = head, eyes, ears, nose, throat; ICF = informed consent form; IGA = Investigator’s Global Assessment; PK = pharmacokinetic; OLE = open-label extension; VIIS = Visual Index for Ichthyosis Severity; WOCBP = women of childbearing potential

- a. Subjects will sign the OLE ICF at the Double-blind Day 90/Week 12 Visit or within 7 days thereafter. All efficacy assessments, safety/tolerability assessments, including clinical laboratory testing and PK from Day 90/Week 12 will be carried over for the OLE and will not be repeated.
- b. Limited physical examination to include HEENT, cardiorespiratory, abdomen, range of motion.
- c. IGA: 0 = clear; 1 = almost clear; 2 = mild; 3 = moderate; 4 = severe
- d. VIIS scale for each body area: chest/abdomen, back, legs, and arms, for a possible overall score = 16.
- e. Roughness (0-4 scale); fissuring assessment on palms/soles: present/absent/number/pain (0-3 scale).
- f. Subjects must be fasting (at least 8 hours)
- g. Subjects who are premenstrual at Screening but begin menses during the course of the study should follow the pregnancy testing schedule for WOCBP correlating to the visit menses began.
- h. Samples for PK will be drawn from all subjects at Day 120 and Day 180. Visits for PK must occur at least 24 hours after the last application of the IP to avoid contamination of the blood samples with any IP that may have remained in the skin after the last application.
- i. Subjects must record days/times of study drug application in the diaries and any areas of skin not treated (e.g., due to local reactions).
- j. All subjects in the OLE will receive trifarotene 200 µg/g. Study drug provided in 50-g tubes (maximum single application is 36 g). Measure study drug tubes before dispensing. Dispense enough additional study drug until the next visit (except at Day 180).
- k. Confirm study drug compliance by measuring tube weight and reviewing diary.

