10.2.2.7 Visit 6 (90 ±7 days) or Early Termination

The following procedures will be performed on Day 90 in the study clinic:

1. Record responses to DLQI and EQ-5D Quality of Life Questionnaires (see Sections 10.3.1.6 and 10.3.1.7 for which version of questionnaire to use).
2. Perform a physical examination.
3. Record vital signs (blood pressure and pulse).
4. Record concomitant medications and concomitant therapies.
5. Record IGA.
6. Record VIIS.
7. Record roughness assessment.
8. Record palm/sole assessment.
9. Record palm/sole assessment of fissuring.
10. Record ectropion score.
11. At sites where the optional photographic substudy is conducted, take photographs of subjects who have provided informed consent for the substudy.
12. Assess local tolerance.
13. Record AEs and review diary.
14. Perform a 12-lead ECG.
15. Perform a urine pregnancy test for WOCBP.
16. Collect blood and urine for routine laboratory tests (subject must be fasting at least 8 hours).
17. Collect a PK blood sample (all subjects).
18. Collect returned study drug tubes; confirm study drug compliance by weighing returned tube contents and reviewing diaries.

For subjects who successfully complete (i.e., have reliable visit attendance and compliance with IP application, in the investigator's opinion) the initial 12 weeks of double-blind treatment and choose to continue into the OLE, this visit will be the first visit of that portion of the study. All efficacy assessments, safety/tolerability assessments, including clinical laboratory testing, PK from Day 90/Week 12 will be carried over to the OLE and will not be repeated. Subjects will have up to 7 days to decide to enter the OLE; if the subject chooses to continue into OLE, the following additional procedures will be done:

1. Have the subject sign OLE-specific informed consent.
2. Measure subject's weight.
3. Instruct subject on study drug application, and advise subjects regarding permitted emollient(s) and/or sunscreen for use on nontreatment days; use of emollient(s) on study drug treatment days within 4 hours before or after study drug application is prohibited.

Remind subjects that at least 24 hours must have elapsed since IP application before the PK draws at the Week 16 and Week 24 Visits, and not to apply IP on visit days until after the visits.

4. Weigh new study drug tubes and dispense enough additional study drug until next visit (only for subjects who choose to continue into the OLE).
5. Dispense study diary.

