10.2.4.1 Telephone Visit (Day 97)

Clinic staff will telephone subject to assess safety (AEs) and to record concomitant medications/therapies. Staff will to instruct subject on study drug application, to advise subjects regarding permitted emollient(s) for use on nontreatment days (use of emollient(s) on study drug treatment days within 4 hours of study drug application is prohibited), and to remind subjects not to apply IP on visit days until after the visit. An unscheduled clinic visit may be performed, if necessary.

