10.2.4.2 Visit 7 (Week 14; Day 104 ± 5 days)

The following procedures will be performed at this study clinic visit:

1. Record concomitant medications and concomitant therapies.
2. Record vital signs (blood pressure and pulse).
3. Record IGA.
4. Record VIIS.
5. Record assessment of roughness.
6. Record palm/sole assessment.
7. Record palm/sole assessment of fissuring.
8. Record ectropion score.
9. Assess and record local tolerance/AEs and review diary.
10. Collect returned study drug tubes; confirm study drug compliance by weighing returned tube contents and reviewing diaries.

11. Weigh new study drug tubes and dispense enough additional study drug until next visit, and new diary.
12. Instruct subject on study drug application, and advise subjects regarding permitted emollient(s) for use on nontreatment days; use of emollient(s) and/or sunscreen on study drug treatment days within 4 hours before or after study drug application is prohibited. Remind subjects that 24 hours must have elapsed since IP application before the subject's next visit. Subjects should not apply IP on visit days until after the visit. at the Week 16 and Week 24 Visits, and not to apply IP on visit days until after the visit.

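### On-treatment OLE contacts are counted from double-blind Day 1 rather than from the first OLE application, so the Day 97 safety call can fall on or before the first open-label 200 µg/g dose

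*Protocol*

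**What the plan says.** The last double-blind visit is "Visit 6 (90 ±7 days) or Early Termination" (Protocol, Section 10.2.2.7). It doubles as the entry point to the extension: "Day 90/Week 12 will be the first visit of the OLE for subjects who choose to continue" (Section 2.2, Table 2-1, footnote b). The same footnote allows a delay: "subjects will have up to 7 days to decide to sign the ICF and begin the OLE". Table 2-2, footnote a, ties the delay to the visit itself: "Subjects will sign the OLE ICF at the Double-blind Day 90/Week 12 Visit or within 7 days thereafter". New tubes are dispensed "only for subjects who choose to continue into the OLE" (Section 10.2.2.7). The Week 12 efficacy, safety and PK results "will be carried over to the OLE and will not be repeated".

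The later contacts keep study-day numbers that run on from Day 1 (Table 2-2; Sections 10.2.4.1 to 10.2.4.6):
- a safety call on Day 97, with no window
- Visit 7 on Day 104 ±5
- Visit 8 on Day 120 ±7
- a call on Day 134
- Visit 9 on Day 150 ±7
- Visit 10 on Day 180 ±7

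Nothing re-anchors them to OLE consent or to the first OLE application. The exception is the follow-up visit (Visit 11), which is set 14 days after the last application (Section 10.2.4.7).

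**The concern.** The OLE calendar appears to copy the double-blind one. Subtracting 90 from Days 97, 104, 120, 134, 150 and 180 gives 7, 14, 30, 44, 60 and 90. The double-blind contacts are on Days 7, 14, 30, 45, 60 and 90. The copy works only if open-label treatment starts on Day 90 exactly, and the protocol's own windows allow it to start earlier or later.

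Safety of 200 µg/g in the extension is a secondary objective (Section 6.2). Section 11.3.1 makes local application-site events an adverse event of special interest because topical retinoids tend to cause them early in treatment. Two groups meet something new at OLE start: former vehicle subjects, who meet trifarotene for the first time, and former 100 µg/g subjects, who step up in strength. For a late starter, the scheduled call meant for the first week of exposure can take place before there is any. The tolerability, laboratory, ECG and PK results reported under one visit label also come from very different lengths of open-label exposure.

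**Working it through.** **Inputs.** Visit 6 is Day 90 ±7 (Section 10.2.2.7). The delay to OLE start is 0 to 7 days, counted from the actual Week 12 visit (Table 2-2, footnote a). The later contact days and windows are as listed above. The first OLE application is taken to be on the day the OLE begins.

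**The plan's own total.** Sections 2.1 and 10.1.1 give a maximum of about 229 days (33 weeks). This is reproduced as 35 screening days + 180 + 14 = 229 days, and 229 / 7 = 32.7 weeks. So the stated maximum makes no allowance for a late Visit 6 or for the decision period.

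**Range of OLE start.** Earliest: 90 − 7 = Day 83, with no delay. Latest: 90 + 7 + 7 = Day 104.

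**Days from first OLE application to each contact.** The shortest interval is the earliest contact day minus 104. The longest is the latest contact day minus 83.

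| Contact | Permitted days | Shortest | Longest | If start is Day 90 and contact nominal |
|---|---|---|---|---|
| Call | 97 | 97 − 104 = −7 | 97 − 83 = +14 | +7 |
| Visit 7 | 99–109 | 99 − 104 = −5 | 109 − 83 = +26 | +14 |
| Visit 8 (first OLE laboratory tests, ECG, PK) | 113–127 | 113 − 104 = +9 | 127 − 83 = +44 | +30 |
| Visit 10 | 173–187 | 173 − 104 = +69 | 187 − 83 = +104 | +90 |

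**How easily the call goes wrong.** With Visit 6 on Day 90 and all 7 days used, the start is Day 97, the day of the call. With Visit 6 on Day 91 and all 7 days used, the start is Day 98, one day after the call. There are 15 × 8 = 120 permitted pairs of Visit 6 day and delay. In 28 of them the start is after Day 97, and in 8 it is on Day 97.

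**How easily Visit 7 goes wrong.** It can precede the first dose only if the start is Day 100 or later. That needs Visit 6 on Day 93 or later with the full delay, or on Day 97 with at least 3 days' delay, and also an early Visit 7. Of 120 × 11 = 1,320 permitted triples, 35 put Visit 7 before the start and 21 on the same day. With Visit 6 on Day 90, Visit 7 is always at least 99 − 97 = 2 days after the start.

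These are counts of permitted calendar combinations, not probabilities. The protocol gives no basis for saying how many subjects would start late.

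**Under event-based timing at the same spacing.** The call is always at +7 days, Visit 7 at +9 to +19, Visit 8 at +23 to +37, and Visit 10 at +83 to +97.

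**The case against.** The seven days are a ceiling, not the planned path. Subjects hear about the extension at Day 30, Day 45 and Day 60, Day 90 is described as the first OLE visit, and Table 9-2 plans OLE dispensing at Day 90. Many subjects may start promptly. That stands, and it is why the permitted ranges should not be read as typical values.

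The seven days could be read as running from nominal Day 90, since footnote a is also attached to the Day 97 column of Table 2-2. The latest start would then be Day 97 and Visit 7 would always follow it. The wording of the footnote favours the actual visit. Even on the narrower reading, the call can fall on the first day of treatment and so say little about OLE exposure.

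Early reactions do not depend on these contacts alone. Subjects are told to report tolerability problems, unscheduled visits are allowed (Section 9.4), and diaries record application-site reactions. Application dates are transcribed to the eCRF (Section 9.5), so exposure time can be recovered in analysis, and there is no formal OLE inference. This is real mitigation. It does not make a scheduled safety call informative when it is placed before exposure, and analysis windowing cannot repair that.

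A reader might infer that about two thirds of entrants begin a retinoid at OLE start. The protocol does not support that. Under 1:1:1 allocation and equal continuation across arms (an assumption), about one third, the former vehicle subjects, begin a retinoid. Former 100 µg/g subjects have already had 12 weeks of trifarotene and only step up.

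**Conclusion.** The point holds, mainly for the Day 97 call. Without any protocol deviation, that call can fall on the day of the first OLE application or up to 7 days before it, and a Visit 6 one day late with the full decision period is enough. The wider effect is the spread in time since OLE start: up to 26 days at Visit 7, 9 to 44 days at Visit 8, and 69 to 104 days at Visit 10, against a stated OLE of up to 12 weeks (84 days). Scheduled early safety follow-up is weakened, chiefly for former vehicle subjects and also for those stepping up from 100 µg/g.

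Three stronger readings are not supported. Visit 7 before dosing is an edge case and does not carry the same weight as the call. Not every OLE contact is tied to Day 1, because Visit 11 already follows the last application. Early reactions would not go unseen, given the unscheduled visits, diaries and self-reporting.

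The conclusion assumes that the 7 days run from the actual Week 12 visit and that the first application is made on the day the OLE begins. If subjects apply later than they consent, the overlap grows.

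**What to change.** Reconcile Tables 2-1 and 2-2 with their footnotes, Section 10.2.2.7 and Sections 10.2.4.1 to 10.2.4.6. Define OLE Day 1 as the date of the first OLE application. Time the on-treatment OLE contacts from it at the existing spacing and windows: calls at 7 and 44 days, and visits at 14 ±5, 30 ±7, 60 ±7 and 90 ±7 days. Leave Visit 11 as already anchored.

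Restate the 229-day maximum in Sections 2.1 and 10.1.1 to allow for the Visit 6 window and the decision period. At nominal visit timing, the latest starter reaches Visit 10 on Day 104 + 90 = 194 and follow-up on Day 194 + 14 = 208. With screening that is 35 + 208 = 243 days.

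The cost is amendment wording and a revised visit calendar, with participation up to 243 − 229 = 14 days longer for the latest starters. No visit, procedure, dose or clinical rule changes. Keeping the present spacing leaves the 90-day calendar against a stated 12 weeks (84 days) of treatment as it is; that difference is a separate matter.
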